Version 6.0		
Protocol Amendment Summary of Changes	The substantiality assessment was revised from referring to Article 2 §2 (13) of the Regulation (EU) No 536/2014 of the European Parliament and the Council of the European Union to Article 10(a) of Directive 2001/20/EC of the European Parliament and the Council of the European Union.	This protocol is still under the directive and it will not transition to the new regulations.
Version 5.0		
5.2, Exclusion Criteria, Criterion 12 10.4, Appendix 4: Washout Requirements Before First IMP Administration	The exclusion criterion and washout period for serious thromboembolic events was updated. The prohibited period for any major thrombotic or embolic event (eg, myocardial infarction, stroke, deep venous thrombosis, or pulmonary embolism) was revised from within 12 months to within 5 years before randomization. Exclusion criterion 12 was renumbered as 12a.	The DSMB monitoring the ARGX-113 ITP program recommended a revision to the washout period for the exclusion of participants with serious thromboembolic events.
7.1, Discontinuation of Trial Intervention	Language was added to clarify that any participant developing a new or recurrent malignancy except basal cell carcinoma will discontinue trial treatment regardless of the relationship to IMP.	The DSMB monitoring the ARGX-113 ITP program recommended a mandatory discontinuation from trial intervention for trial participants with an initial or recurrent malignancy.
1.3, Schedule of Activities, Table 1 10.9, Appendix 9, Table 5, Schedule of Activities 8.6, Pharmacokinetics	Footnote n regarding when PK/PD/ADA samples should be collected was revised from within 2 hours to within the same day, before IMP administration. Table 4 was renumbered as Table 5.	The revision allows additional flexibility for trial sites.
2.3.1, Risk Assessment	Table 2 of potential risks and mitigation strategies was added.	The table succinctly addresses the trial risks and mitigation strategies.
5.1, Inclusion Criteria, Criterion 8b 10.6.2, Contraception Guidance	The contraception requirement for male participants was removed. Inclusion criterion 8a was renumbered as 8b. Section 10.6.2.2 Male Contraception was deleted.	This global change was made to all ARGX-113 studies based on emerging nonclinical data indicating that efgartigimod has a low risk of teratogenicity/fetotoxicity.


3, Objectives and Endpoints 9.5.7, Other Secondary Endpoint Analyses Not Subject to Alpha Control
	
An efficacy objective was added to compare efgartigimod PH20 SC to placebo PH20 SC in IWG response and initial response, measuring the proportions of participants with an IWG response, an IWG complete response, and an initial response.
	
The revision was made to align with the SAP.

3, Objectives and Endpoints 8.12, Immunogenicity Assessments 10.3, Appendix 3, Table 4
	
Text reading “and titers of NAb against efgartigimod and/or rHuPH20 in the overall population” was revised to “and titers of NAb against rHuPH20 in the overall population.” Table 3 was renumbered as Table 4.
	
The text was not correct. Titers are determined for only the PH20 NAb assay, not the efgartigimod NAb assay.

8.3.2, Vital Signs
	
Instructions for taking blood pressure were amended to include that participants should be seated and rested.
	
The updated instructions match site practices and prevent protocol deviations.

10.4, Appendix 4: Washout Requirements Before First IMP Administration
	
Anti-CD20 therapy (eg, rituximab) with a washout of 6 months before randomization was added.
	
This requirement was added to match inclusion criterion 7.

2.2, Background 1.1, Synopsis
	
ARGX-113-1801 was added to the list of sources of clinical history.
	
Additional data were available in ARGX-113-1801 to support product development.

2.3.2, Benefit Assessment
	
Lengthy description was replaced with language that directs the reader to the benefit/risk assessment in the current IB.
	
The IB is the primary repository for updated product data.

5.1, Inclusion Criteria, Criterion 2
	
The age of consent inclusion criterion was revised to state that participants should be at least the local legal age of consent for clinical trials when signing the ICF. Inclusion criterion 2 was renumbered as 2a.
	
The revision matches global requirements for the legal participation age.

1. PROTOCOL SUMMARY

1.1. Synopsis

Protocol Title:

A Phase 3, Multicenter, Randomized, Double-Blinded, Placebo-Controlled Trial to Evaluate the Efficacy and the Safety of Efgartigimod (ARGX-113) PH20 Subcutaneous in Adult Patients With Primary Immune Thrombocytopenia

Short Title:

Not applicable

Indication:

Primary immune thrombocytopenia (ITP)

Trial Sites/Countries:

This is a global, multicenter trial

Target Population:

Adult patients with persistent or chronic primary ITP, who have an average platelet count of $<30 \times 10^9/L$, and, at the start of the trial taking concurrent ITP treatment(s) and having received at least 1 prior therapy for ITP in the past, or not taking treatment for ITP but having received at least 2 prior treatments for ITP.

Test Product, Dose, and Mode of Administration:

Test product:

Efgartigimod 180 mg/mL coformulated with 2000 U/mL recombinant human hyaluronidase PH20 (rHuPH20) for subcutaneous (SC) administration (efgartigimod PH20 SC)

Dose:

Each dose of efgartigimod PH20 SC will include 1000 mg efgartigimod per injection.

Mode of administration:

Subcutaneous injection

Comparator, Dose, and Mode of Administration:

Comparator:

Placebo PH20 SC

Dose:

Placebo with rHuPH20 for SC administration (placebo PH20 SC)

Mode of administration:

Subcutaneous injection

Rationale:

This phase 3 trial aims to evaluate the efficacy, safety, and effect on the quality of life (QoL) and patient-reported outcomes (PRO) of efgartigimod PH20 administered as SC injections in adult patients with primary ITP who have had an insufficient response or who are intolerant to existing ITP treatments, evidenced by an average platelet count that is below the clinically accepted level for intervention ($<30 \times 10^9/L$).

Participants classified as having persistent primary ITP (between 3 and 12 months since diagnosis) and chronic primary ITP (greater than 12 months since diagnosis) will be recruited. The diagnosis of primary ITP should be supported by a response to a prior ITP therapy other than thrombopoietin receptor agonists (TPO-RAs). At the start of the trial, the participants are either taking concurrent ITP treatment(s) and have received at least 1 prior therapy for ITP in the past, or the participants are not taking treatment for ITP but have received at least 2 prior treatments for ITP. If participants are receiving concurrent ITP therapies at baseline, these therapies should have been maintained at a stable dose and dosing frequency for 4 weeks before randomization.

Treatments for ITP are often used in combination and efgartigimod has the potential to be used in combination with other ITP therapies or offer a new stand-alone modality. Therefore, participants with and without concurrent ITP therapy will be enrolled. Experience to date of efgartigimod treatment in combination with steroids and immunosuppressants in phase 2 and phase 3 trials in primary ITP and myasthenia gravis (MG) have not raised any safety concerns with these combinations of treatments.

Results of the phase 1 trials in healthy subjects (ARGX-113-1501, ARGX-113-1702), the phase 2 trials in participants with ITP (ARGX-113-1603) and MG (ARGX-113-1602), the phase 3 trials in participants with MG (ARGX-113-1704 and ARGX-113-1705) and ITP (ARGX-113-1801), as well as pharmacokinetic/pharmacodynamic (PK/PD) modeling analysis, indicate that a dose of 10 mg/kg efgartigimod, administered weekly (qw) through intravenous (IV) infusion achieved close to maximal immunoglobulin G (IgG) reduction (PD effect), resulted in a reduction of pathogenic autoantibodies, and was associated with clinical efficacy in both participants with ITP and participants with MG. Furthermore, this dose was safe and well-tolerated in all populations.

In order to allow for a convenient SC administration with efgartigimod to achieve the targeted exposure and PD effect, efgartigimod will be coformulated with rHuPH20. rHuPH20 is being used in coformulations with approved therapeutic antibodies to facilitate SC injection with volumes larger than 2 mL.

In designing the current phase 3 trial, a dose of 1000 mg efgartigimod administered as qw or every other week (q2w) SC injections coformulated with rHuPH20 was predicted to result in a comparable effect on IgG levels as with 10 mg/kg IV administered qw or q2w.

No significant safety findings have been identified to date with efgartigimod administered SC in combination with rHuPH20 in completed or ongoing trials.

Objectives and Endpoints

Objectives and Endpoints:	
Objectives	Endpoints
Primary	

 To evaluate the efficacy of efgartigimod PH20 SC compared to placebo PH20 SC in achieving a sustained platelet count response in patients with chronic primary ITP, with a sustained platelet count response defined as platelet counts of $\geq 50 \times 10^9/L$ for at least 4 of the 6 visits between week 19 and week 24 of the trial 
Note: “week” instead of “visit” is used in the endpoints, ensuring that the platelet count of the end-of-treatment visit is regarded as week 24 platelet count (eg, platelet count after 19 weeks of treatment corresponds with platelet count of visit 20)
	
 Proportion of patients with chronic ITP with a sustained platelet count response defined as achieving platelet counts of $\geq 50 \times 10^9/L$ for at least 4 of the 6 visits between week 19 and week 24 of the trial
Secondary	

 To evaluate the efficacy of efgartigimod PH20 SC compared to placebo PH20 SC in overall platelet count response 	
 Extent of disease control defined as the number of cumulative weeks over the planned 24-week treatment period with platelet counts of $\geq 50 \times 10^9/L$ in the chronic ITP population (Key Secondary Endpoint 1) Proportion of patients in the overall population (chronic and persistent ITP) with a sustained platelet count response defined as achieving platelet counts of $\geq 50 \times 10^9/L$ for at least 4 of the 6 visits between week 19 and week 24 (Key Secondary Endpoint 2) Proportion of patients in the overall population achieving platelet counts of $\geq 50 \times 10^9/L$ for at least 6 of the 8 visits

	
between week 17 and 24 of the trial (Key Secondary Endpoint 3)
 
 • Proportion of patients in the overall population with overall platelet response defined as achieving a platelet count of $\geq 50 \times 10^9/L$ on at least 4 occasions at any time during the 24-week treatment period • Extent of disease control defined as the number of cumulative weeks until week 12 with platelet counts of $\geq 50 \times 10^9/L$ in the overall population • Proportion of patients in the overall population with overall platelet response defined as achieving a platelet count of $\geq 50 \times 10^9/L$ on at least 4 occasions at any time until week 12 • Mean change from baseline in platelet count at each visit in the overall population • Time to response defined as the time to achieve 2 consecutive platelet counts of $\geq 50 \times 10^9/L$ in the overall population • The number of cumulative weeks over the planned 24-week treatment period with platelet counts of $\geq 30 \times 10^9/L$ and $\geq 20 \times 10^9/L$ above baseline in the overall population • In patients with baseline platelet count of $< 15 \times 10^9/L$, the number of cumulative weeks over the planned 24-week treatment period with platelet counts of $\geq 30 \times 10^9/L$ and $\geq 20 \times 10^9/L$ above baseline in the overall population

 • To evaluate the incidence and severity of bleeding events while receiving treatment with efgartigimod PH20 SC compared to placebo PH20 SC 	
 • Incidence and severity of the World Health Organization (WHO)-classified bleeding events in the overall population (Key Secondary Endpoint 4)

 • To evaluate the efficacy of efgartigimod PH20 SC compared to placebo PH20 SC in International Working Group (IWG) response 	
 • Proportion of patients with an IWG response • Proportion of patients with an IWG complete response

	
 Proportion of patients with an initial response

 To evaluate the safety and tolerability of efgartigimod PH20 SC administered qw or q2w compared to placebo PH20 SC 	
 Incidence and severity of adverse events (AEs), AEs of special interest (AESIs), and serious AEs (SAEs) in the overall population Vital signs, electrocardiogram (ECG), and laboratory assessments in the overall population

 To evaluate the use of rescue treatment and changes in concurrent ITP therapy while receiving treatment with efgartigimod PH20 SC compared to placebo PH20 SC 	
 Rate of receipt of rescue therapy (rescue per patient per month) in the overall population Proportion of patients for whom dose and/or frequency of concurrent ITP therapies have increased at week 12 or later in the overall population

 To evaluate the effects of efgartigimod PH20 SC treatment on QoL measures and PRO compared to placebo PH20 SC 	
 Change from baseline in PRO (Functional Assessment of Chronic Illness Therapy Fatigue Scale [FACIT-Fatigue], Functional Assessment of Cancer Therapy questionnaire-Th6 [Fact-Th6]) and QoL (Short Form-36 [SF-36]) at planned visits in the overall population

 To assess the immunogenicity of efgartigimod and rHuPH20 	
 Incidence and prevalence of antibodies to efgartigimod and/or rHuPH20 in the overall population Titers of antibodies to efgartigimod and/or rHuPH20 in the overall population Presence of neutralizing antibodies (NAb) against efgartigimod and/or rHuPH20, and titers of NAb against rHuPH20 in the overall population

 To assess the PK of efgartigimod PH20 SC 	
 Serum efgartigimod concentration observed predose (C_{trough}) in the overall population

 To assess the PD effects of efgartigimod PH20 SC 	
 Pharmacodynamics markers: total IgG and antiplatelet antibody levels in the overall population

Exploratory	

 • [REDACTED] 	
 ■ [REDACTED]

 • [REDACTED] 	
 ■ [REDACTED]

 • [REDACTED] 	
 ■ [REDACTED] ■ [REDACTED] ■ [REDACTED]

 • [REDACTED] 	
 ■ [REDACTED]

Overall Design:

This is a phase 3, multicenter, randomized, double-blinded, placebo-controlled, parallel-group trial to evaluate the efficacy, safety, and effect on QoL/PRO of efgartigimod PH20 SC treatment in adult patients with primary ITP.

The target population is adult patients with persistent or chronic primary ITP, having an average platelet count of $<30 \times 10^9/L$, and, at the start of the trial taking concurrent ITP treatment(s) and having received at least 1 prior therapy for ITP in the past, or not taking treatment for ITP but having received at least 2 prior treatments for ITP. If participants are receiving concurrent ITP therapies at baseline, these therapies should have been maintained at a stable dose and dosing frequency for 4 weeks before randomization.

Disclosure Statement:

ARGX-113-2004 is a double-blinded, randomized, parallel-group trial to evaluate the efficacy, safety, and effect on QoL/PRO of fixed doses of efgartigimod PH20 SC, compared to placebo PH20 SC.

Number of Participants:

Approximately 180 participants with chronic ITP and up to 39 participants with persistent ITP will be randomized in a 2:1 ratio to receive efgartigimod PH20 SC or placebo PH20 SC, respectively. Recruitment will end when 180 participants with chronic ITP have been randomized.

Participants will be stratified according to the following factors:

- History of splenectomy (yes versus no)
- Receiving concurrent ITP therapies at baseline (yes versus no)

Intervention Groups and Duration:

The total maximum trial duration per participant is up to 35 weeks:

- Up to 2 weeks of screening
- 24 weeks treatment period
- End-of-treatment visit: 1 week after visit 24
- 8 weeks of follow-up

After confirmation of eligibility, the participants enter a 24-week treatment period and will be randomized to receive efgartigimod PH20 SC or placebo PH20 SC, qw from visits 1 to 4 and then from visits 5 to 16 either qw or q2w, adjusted according to their platelet counts. From visits 17 to 24, participants will be fixed on the dose schedule they were receiving at visit 16 or at the last visit at which the investigational medicinal product (IMP) was administered before visit 16 (ie, either qw or q2w).

All participants or their caregivers (as defined in Section 10.10) will be invited to receive training to (self-)administer the IMP while under supervision at least 4 times in the last 10 weeks, until they are capable of and comfortable with the (self-)administration ([self-]administration without supervision is foreseen only in the open-label extension trial ARGX-113-2005, not in ARGX-113-2004).

If the participant or his/her caregiver successfully completes the training to the satisfaction of the authorized staff, the participant or his/her caregiver, then the participant or his/her caregiver may administer the next injections at the trial site under the supervision of the authorized staff. The training must be documented in the participant's source documents and eCRF.

[figure not shown]
Participants who complete the 24-week randomized trial period will perform the end-of-treatment visit and can enter the open-label extension trial, ARGX-113-2005. If a participant has had an SAE during ARGX-113-2004, his/her eligibility for ARGX-113-2005 should be evaluated by the investigator. The platelet counts from ARGX-113-2004 will be taken into account to assess dosing frequency in ARGX-113-2005.

Participants who complete the 24-week trial period but do not enter the open-label extension trial, or participants who discontinue the trial early, with the exception of participants who withdraw their consent, will be followed up for 8 weeks for ongoing safety and efficacy monitoring.

For participants who discontinue the trial early, all the assessments listed for the early discontinuation visit specified in the Schedule of Activities (Section 1.3), will be performed.

Data Monitoring Committee: yes (see Section 10.1.5.1)

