1.2 STUDY ENDPOINTS

1.2.1 *Primary endpoint*

The primary endpoint is the proportion of patients with chronic ITP with a sustained platelet count response defined as achieving platelet counts of at least $50 \times 10^9/L$ for at least 4 of the 6 visits between week 19 and 24 of the study.

Participants who discontinue treatment prior to visit 24 due to lack of efficacy (e.g. more than 3 occurrences of rescue therapy) or due to an AE, and who have not achieved sustained platelet count response between week 19 and 24, are considered non-responders. Participants who receive rescue therapy at week 12 or later, or for whom dose and/or frequency of concurrent ITP therapies have increased at week 12 or later, are also considered non-responders.

1.2.2 *Secondary endpoints*

Key Secondary Efficacy Endpoints Subject to Alpha Control:

- Extent of disease control defined as the number of cumulative weeks over the planned 24-week treatment period with platelet counts of $\geq 50 \times 10^9/L$ in the chronic ITP population.
- Proportion of patients in the overall population (chronic and persistent ITP) with a sustained platelet count response defined as achieving platelet counts of at least $50 \times 10^9/L$ for at least 4 of the 6 visits between week 19 and 24 of the study.
- Proportion of patients in the overall population achieving platelet counts of at least $50 \times 10^9/L$ for at least 6 of the 8 visits between week 17 and 24 of the study.
- Incidence and severity of the WHO-classified bleeding events in the overall population.

Other Secondary Endpoints Not Subject to Alpha Control (overall population):

- Proportion of patients with overall platelet response defined as achieving a platelet count of $\geq 50 \times 10^9/L$ on at least 4 occasions at any time during the 24-week treatment period.
- Extent of disease control defined as the number of cumulative weeks until week 12, with platelet counts of $\geq 50 \times 10^9/L$.

	Statistical Analysis Plan	
ARGX-113-2004	Final analysis	Final 1.0 of 7NOV2023

- Proportion of patients with overall platelet response defined as achieving a platelet count of $\geq 50 \times 10^9/L$ on at least 4 occasions at any time until week 12.
- Mean change from baseline in platelet count at each visit.
- Time to response defined as the time to achieve 2 consecutive platelet counts of $\geq 50 \times 10^9/L$.

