ARGX-113-2004	Final analysis	Final 1.0 of 7NOV2023

- Scale score = mean of all available converted item scores
A scale score cannot be calculated if less than 50% of the items of the scale are answered. Otherwise, scores for missing items will be imputed with the arithmetic average of the non-missing item scores. Converted item scores are not rounded when calculating the scale score.

- 6) Rate of receipt of rescue therapy: number of times rescue therapy is given per month, calculated as $\frac{\text{Total number of occurrences}}{\text{total days in treatment phase}} \times 30.4$

Occurrence: a period of maximum 5 days where 1 or more rescue treatments are administered simultaneously or consecutively to the study participant. The start date/time of the occurrence is the start of the administration of the first rescue treatment. If this period exceeds the maximum of 5 days, a new occurrence will be assigned, with start date/time of the occurrence being the start date 5 days after the initial occurrence start date.

- 7) Proportion of participants for whom dose and/or frequency of concurrent ITP therapies have increased at week 12 or later.

Derivation: a participant is counted if (start date concurrent ITP therapy \geq lower limit ADY of analysis visit corresponding to week 12) AND (dose > previous dose of the specific ITP therapy OR frequency > previous frequency of the specific ITP therapy OR new ITP therapy). Note: Dose and frequency will always be considered in combination (ie, mean daily doses will be compared).

- 8) Time to platelet count response defined as the time to achieve 2 consecutive platelet counts of $\geq 50 \times 10^9/L$.

Derivation: It will be calculated as the difference between the first assessment date at which the condition '2 consecutive platelet counts $\geq 50 \times 10^9/L$ ' is fulfilled, taking into account all platelet count measurements (also the unscheduled ones), and first IMP intake date.

Time to platelet count response (days) = date (first assessment) – first IMP date + 1:

Table 9: Definition for Time to Platelet Count

Response Situation	Time to Platelet Count Response	Outcome ^d
No occurrence of platelet count of $\geq 50 \times 10^9/L$	Date of last available platelet count ^c – first IMP date ^b + 1	Censored
Early discontinuation of treatment (prior to W24) due to lack of efficacy or due to AE ^a	Early treatment discontinuation date – first IMP date ^b + 1	Censored

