Summary statistics will be provided for the different definitions of number of bleeding events in the overall population. A frequency tabulation will be provided of the number and percentage of bleeding events and repeated for the subgroup on sustained platelet count response (week 19 – 24). The overall severity score at each analysis visit and the worst-case overall severity score will be tabulated.

Summary statistics will be provided in terms of actual values and changes from baseline for PRO scores (FACIT-Fatigue, FACT-Th6) and QoL (SF-36, ITP-PAQ) in the overall population. All analysis visits as expected per SoA (including the follow-up phase) will be shown.

Summary statistics will be provided for the rate of receipt of rescue therapy in the overall population. A frequency tabulation will be provided of the number of rescue therapies (occurrences) received.

Frequency tabulations will be provided of the proportion of participants for whom dose and/or frequency of concurrent ITP therapy have increased at week 12 or later.

KM estimates will be provided for time to platelet count response ($\geq 50 \times 10^9/L$ and $\geq 100 \times 10^9/L$) and time to platelet count $\geq 50 \times 10^9/L$ or $\geq 100 \times 10^9/L$ in the overall population. KM curves and median time to platelet count response will be displayed by randomized treatment.

Summary statistics will be provided in terms of actual values and changes from baseline for IPF# and IPF% in the overall population. All analysis visits as expected per SoA (including the follow-up phase) will be shown.

Statistical inference will be conducted as described below. All statistical comparisons will be made using two-sided tests at the 0.05 significance level unless specifically stated otherwise. Sensitivity analyses will be done for the primary and key secondary endpoints by using the PP population (PP-chronic). The primary and first key secondary endpoint will also be repeated by use of approach 2 for imputing missing values as sensitivity analysis. A complementary analysis using the treatment policy strategy will be done on the primary and the first key secondary endpoint. Furthermore, a complementary analysis will be done on the first key secondary endpoint extent of disease control using a Cox proportional hazards regression model.

	Statistical Analysis Plan	
ARGX-113-2004	Final analysis	Final 1.0 of 7NOV2023

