The primary endpoint, sustained platelet count, will be analyzed using a Cochran-Mantel-Haenszel statistic stratified for each stratum formed by the combination of the stratification factors. The stratification factors will be history of splenectomy (yes versus no) and receiving concurrent ITP therapies at baseline (yes versus no) and baseline platelet count level category ($< 15 \times 10^9/L$ versus $\geq 15 \times 10^9/L$). The treatment effect will be presented as the odds ratio together with its exact 95% confidence interval (CI)¹⁵ and 2-sided p-value. The MH estimator¹⁶ will be used for the odds ratio (OR), except in case of empty cells for all strata within one treatment, in which case the logit estimator¹⁷ will be used. An OR of more than 1 represents a higher response rate for efgartigimod compared to placebo. In addition, an adjusted difference of the proportions with its 95% confidence (Klingenberg approach) will be provided.

Missing data due to a reason of one of the main intercurrent events as described above (see section 4.1.2.1) will be analyzed as a non-responder (composite variable strategy). Missing data for other reasons will be imputed as described in section 4.1.2.5, approach 1. The analysis will be repeated with approach 2 as sensitivity analysis for the primary endpoint.

	Statistical Analysis Plan	
ARGX-113-2004	Final analysis	Final 1.0 of 7NOV2023

All secondary endpoints related to sustained platelet count response, overall platelet count response, and IWG derived endpoints (ie, complete IWG response, IWG response and initial response) will be analyzed in the same manner as this primary endpoint.

For the primary endpoint only, the analysis will be repeated where the main intercurrent events will be handled by using the ‘treatment policy’ strategy (see section 4.1.2.1).

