14.2.3.4	Bleeding events (≥ 1 WHO scale): Descriptive Statistics of the Number of Events by Stratification Factor, Baseline Platelet Count and Overall in the Overall Population	FAS	TL
14.2.3.5	Bleeding events (≥ 2 WHO scale): Stratified Mann-Whitney Analysis in the Overall Population	FAS	
14.2.3.6	Bleeding events (≥ 2 WHO scale): Descriptive Statistics of the Number of Events in the Overall Population	FAS	
14.2.4.1	PRO (FACIT-Fatigue): Changes from Baseline in FACIT-Fatigue Scores – MMRM	FAS	TL
14.2.4.2	PRO (FACIT-Fatigue): Descriptive Statistics of Actual Values and Changes from Baseline	FAS	TL
14.2.4.3	PRO (FACT-Th6): Changes from Baseline in Fact-Th6 Scores – MMRM	FAS	
14.2.4.4	PRO (FACT-Th6): Descriptive Statistics of Actual Values and Changes from Baseline	FAS	
14.2.4.5	QoL (SF-36): Changes from Baseline in SF-36 Scores – MMRM	FAS	
14.2.4.6	QoL (SF-36): Descriptive Statistics of Actual Values and Changes from Baseline	FAS	
14.2.4.7	QoL (ITP-PAQ): Changes from Baseline in ITP-PAQ Scores – MMRM	FAS	
14.2.4.8	QoL (ITP-PAQ): Descriptive Statistics of Actual Values and Changes from Baseline	FAS	
14.2.5.1	Rate of Receipt of Rescue Therapy: Descriptive Statistics of Actual Values (Occurrences/Month) in the Overall Population	FAS	
14.2.5.2	Receipt of Rescue Therapy: Frequency Tabulation of Total Number of Rescue Therapy Occurrences	FAS	TL
14.2.6.1	Change in ITP therapy: Frequency Tabulation in the Overall Population	FAS	

	Statistical Analysis Plan	
ARGX-113-2004	Final analysis	Final 1.0 of 7NOV2023

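### The secondary objective comparing rescue use and changes in concurrent ITP therapy with placebo has no prespecified between-arm estimate or between-arm confidence interval for either endpoint

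*Protocol*

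**What the plan says.** The objective appears in the protocol synopsis, in protocol section 3 and in SAP 1.1: "To evaluate the use of rescue treatment and changes in concurrent ITP therapy while receiving treatment with efgartigimod PH20 SC compared to placebo PH20 SC". It carries two endpoints, both in the overall population. SAP 1.2.2 lists them under "Other Secondary Endpoints Not Subject to Alpha Control (overall population").

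SAP 4.1.2.3 derives both. Item 6 defines the rescue rate as the "number of times rescue therapy is given per month", that is, occurrences divided by days in the treatment phase, times 30.4. Item 7 defines who counts as having concurrent ITP therapy increased at week 12 or later.

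SAP 4.1.3 then plans the following:

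- For the rescue rate: "Summary statistics will be provided for the rate of receipt of rescue therapy in the overall population".
- For the count of rescue occurrences: a table of how many each participant had, by arm.
- For therapy escalation: "Frequency tabulations will be provided of the proportion of participants for whom dose and/or frequency of concurrent ITP therapy have increased at week 12" (the sentence goes on to take in the weeks after that).

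The table list in SAP 8.1 agrees. Table 14.2.5.1 holds descriptive statistics of the rescue rate, 14.2.5.2 is a frequency tabulation of rescue occurrences, and 14.2.6.1 is "Change in ITP therapy: Frequency Tabulation in the Overall Population".

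**The concern.** The objective asks for a comparison, but the planned output is one column per arm. No difference, ratio or between-arm interval is prespecified for either endpoint.

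Both endpoints bear directly on treatment benefit. Under the protocol, rescue needs a low platelet count plus a bleeding risk, bleeding, wet purpura or urgent surgery. Therapy escalation from week 12 is allowed for insufficient response. From week 12 both events also enter the non-response rule of the primary endpoint, so their separate contrasts would help in reading the primary result.

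If no contrast is fixed in advance, any effect quoted later (any rescue, rate difference or rate ratio; crude or stratified) will have been chosen after unblinding.

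**Working it through.** **1. Which comparative objectives get a between-arm method?** The objectives worded as a comparison with placebo, set against the SAP methods:

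| Objective | Planned analysis |
|---|---|
| Platelet response (primary and secondary) | Stratified CMH (SAP 4.1.3.2), stratified Mann-Whitney (4.1.3.4), MMRM (4.1.3.5), Cox (4.1.3.6) |
| Bleeding | Stratified Mann-Whitney (4.1.3.4) |
| IWG response | Stratified CMH (4.1.3.2) |
| PRO and QoL | MMRM (4.1.3.5) |
| Safety | Descriptive, and protocol 9.5.9 says so |
| Rescue use and therapy changes | Summary statistics and tabulations (4.1.3); no inferential section names either endpoint |

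The CMH section extends the primary method to "All secondary endpoints related to sustained platelet count response, overall platelet count response, and IWG derived endpoints", and neither endpoint here belongs to that group. The Agresti-Min limits for differences in SAP 4.1.3 are attached to the platelet response tabulations. Redaction does not explain the gap, because the relevant text and the three table titles are visible.

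**2. What can be recovered from the planned tables?** SAP 2.4.3 presents tables per treatment, and SAP 2.4.1 gives n, mean and SD. A crude risk difference and a crude difference in mean rates, each with a 95% CI, can therefore be worked out by hand. A stratified estimate of the kind given to the other response endpoints cannot, because these tables are not broken down by stratum.

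**3. How precise would a contrast be?** The plan states no figure to reproduce and gives no expected rates for either endpoint, so all rates below are assumptions. Sample size: 180 + 39 = 219, split 2:1 into 146 and 73. This is an upper figure, since the persistent group is capped at 39.

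*Therapy increase.* Wald half-width = 1.96 × √[p₁(1−p₁)/146 + p₂(1−p₂)/73].

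- 5% vs 15%: 1.96 × √(0.000325 + 0.001747) = 8.9 points
- 10% vs 20%: 1.96 × √(0.000616 + 0.002192) = 10.4 points
- 10% vs 25%: 1.96 × √(0.000616 + 0.002568) = 11.1 points
- 15% vs 30%: 1.96 × √(0.000873 + 0.002877) = 12.0 points

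So 15% vs 30% gives −15 points (about −27 to −3), and 10% vs 20% gives −10 (about −20 to 0).

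*Rescue, difference in mean monthly rate.* Half-width = 1.96 × SD × √(1/146 + 1/73) = 1.96 × SD × 0.143. An assumed SD of 0.2 gives ±0.06 per month; an SD of 0.6 gives ±0.17.

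*Rescue, rate ratio.* Assume 0.06 vs 0.10 per month over 169/30.4 = 5.56 months. Expected occurrences are 146 × 0.06 × 5.56 = 48.7 and 73 × 0.10 × 5.56 = 40.6, and the ratio is 0.60. The SE of the log ratio is √[φ(1/48.7 + 1/40.6)], where φ is the overdispersion factor.

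- φ = 1: 95% CI 0.40 to 0.91
- φ = 2: 0.33 to 1.08
- φ = 3: 0.29 to 1.23

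Whether the interval excludes 1 depends on how overdispersion is handled, so the method is worth fixing in advance. Exposure matters as well. One occurrence in 169 days is a rate of 30.4/169 = 0.18 per month, but one in a treatment phase that ended on day 29 is 30.4/29 = 1.05. An unweighted mean of individual rates counts both participants equally.

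**The case against.** Descriptive reporting of low-tier secondary endpoints is a defensible choice. The safety objective uses the same comparative wording and is analysed descriptively. Protocol 9.5 calls itself a summary of the most important endpoints and leaves detail to the SAP, so the silence of protocol 9.5.7 is not a defect in itself. Both events also reach formal between-arm tests: through the non-response rule of the primary endpoint, the weeks counted in the first key secondary endpoint, and the events in its complementary Cox analysis. Intercurrent events are tabulated (14.2.7.1), and rescue is tabulated by category in three analysis sets (14.1.2.11.1 to 14.1.2.11.3).

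Most of this stands, and it limits the point. It does not remove it. The protocol states that the safety analyses are descriptive; no passage says this of the rescue objective. Inside the composites, the two events are merged with platelet counts and other events, so no separate effect emerges.

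A reader might infer that the objective cannot be answered at all, or that the tables cannot tell a clear effect from a borderline one. The documents do not support that: the arms are randomized, shown side by side, and a crude contrast follows from the tables. A reader might also infer that no confidence interval is planned. That is too broad. SAP 2.4.1 can be read as adding within-arm 95% CIs to efficacy summaries, and protocol 9.1.2 promises 95% CIs in general. What is missing is a between-arm interval.

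**Conclusion.** The point holds as a gap in prespecified estimation. Two secondary endpoints under a comparative objective have no planned treatment effect and no between-arm precision, while the other comparative efficacy objectives do. The objective is answered descriptively only. Because both endpoints lie outside the testing hierarchy, the primary conclusion and type I error control are unaffected.

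The conclusion about the gap rests on the text alone. The size does not: the half-widths of about 9 to 12 points, and the rate-ratio intervals, depend on assumed rates and on reaching 146 versus 73. They show what a planned contrast would deliver, and are not a measure of harm from the present plan. This is a cheap improvement worth making.

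**What to change.** - In SAP 4.1.3.2, add the endpoint for concurrent ITP therapy increased at week 12 or later to those analysed like the primary endpoint: stratified CMH odds ratio and adjusted difference, each with 95% CI.
- For the rescue rate, add one between-arm contrast with 95% CI that accounts for treatment-phase time and overdispersion. An example is a rate ratio from a negative binomial model of occurrences with log time as offset; name a simpler rate difference as the fallback if events are sparse.
- Label both as nominal and outside the testing hierarchy.

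If the sponsor prefers to keep the present output, the SAP should state that this objective is descriptive.

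The cost is two extra tables, SAP wording and two more nominal results. The CMH code is already planned. A negative binomial model is not among the methods listed in the SAP code appendix (9.1), so the rate contrast needs a small amount of new code. No new data are required.
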